#### **II.Background and Rationale**

Language impairment (LI) is a high-incidence developmental disability that significantly elevates a child's susceptibility for peer maltreatment, including exclusion from peer social networks and victimization by peers. Studies find, for instance, that nearly 40% of preschoolers with LI are excluded from their classroom social network (Justice, Chen, Jiang, Tambyraja, & Logan, 2019) and a similar percentage of primary-grade pupils with LI are regularly victimized by their peers (Conti-Ramsden & Botting, 2004). These circumstances reflect in part the relatively poor social competence and pragmatic-language skills of children with LI (Longobardi, Spataro, Frigerio, & Rescorla, 2016), but also the socialization processes that characterize classroom settings. Specifically, as early as the preschool years, children demonstrate strong homophilic behaviors in establishing peer relationships in their classrooms (Chen, Lin, Justice, & Sawyer, 2019), preferring to play with others of the same gender, age, skill levels, and disability status. In preschool settings, children with LI tend to interact most frequently with other children with LI, even in inclusive settings serving children with disabilities and typically developing peers (Justice, Chen, et al., 2019).

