#### **g. Data Analysis**

Aim 1 investigates the effects of peer-mediated PRT on the peer interactions and social status (indicated by individual centrality) within the classroom social network for children with LI. We assess this aim based on 6 to 24 repeated measurements for each outcome variable using multilevel growth models (Raudenbush & Bryk, 2002) to investigate changes in key outcomes over the school year and to accommodate the wait-list experimental design. Longitudinal measurements will be nested within participants and predicted by the time of measurement as well as time-specific intervention status. We include interaction terms between time of measurement and intervention status so that any accelerating or decelerating effects of intervention can be captured. In all models, we control for relevant covariates to increase precision of parameter estimates and power (Hox, Moerbeek, & Van de Schoot, 2010; Raudenbush, Martinez, & Spybrook, 2007). To assess treatment effects on peer interactions, we use the number of peer interaction, number of appropriate peer play, and duration of peer talk for the focal children as the outcome variables in the growth models. Depending on the distribution of the variables, appropriate linear or generalized linear models (e.g., Poisson) will be fitted. To examine treatment effects on social status, we compare the trajectories of individual centrality for the focal children and their classmates, controlling for classroom-level variation. Specifically, intervention effects are tested on key components of the trajectories, such as intercept, linear slope and quadratic slope (i.e., the slowing or acceleration of growth). The growth curves for different groups (treatment, wait-list control, and peer) can then be estimated. Aim 2 determines the extent to which peer-mediated PRT contributes to focal children's social, behavioral, and linguistic skills via the mediation of improved socialization experiences. For this aim, we employ multivariate latent growth models, where latent growth curves of socialization indices and child skills can be modelled simultaneously and the relationships between latent growth parameters examined. In particular, two latent slopes (fall and spring) will be specified for the socialization growth curve to capture the differential growth rate with and without intervention; intervention status will be used as a predictor of the two socialization slopes. Due to the sample size limitation, we will examine one socialization index and one skill variable at a time. We will focus on the following pathways: (a) effect of intervention on focal children's socialization experiences at fall, winter, and spring; and (b) effects of socialization experiences on child skills at fall, winter, and spring. Paths (a)\*(b) allow us to test the indirect effects of PRT on social, behavioral, and linguistic skills. To estimate the mediation effect, we use the product-of-coefficient approach (MacKinnon, Lockwood, Hoffman, West, & Sheets, 2002) with a bootstrapping procedure (Preacher & Hayes, 2004, 2008). This method does not require the assumption of normality for the sampling distribution of the product-of-coefficient. Finally, Aim 3 examines changes in classroom social network dynamics over the school year, and tests the effects of peer-mediated PRT on peer socialization at the classroom level. To address this aim,

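### Aim 2 judges PRT's contribution to skills only by a mediated product whose second path is not randomised, and no analysis compares the skills between randomised arms

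*Combined protocol and SAP*

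**What the plan says.** Section III.g (Data Analysis) states the question: "Aim 2 determines the extent to which peer-mediated PRT contributes to focal children's social, behavioral, and linguistic skills via the mediation of improved socialization experiences". The method is a multivariate latent growth model, taking one socialization index and one skill at a time. For path (a), "intervention status will be used as a predictor of the two socialization slopes". Path (b) is described as "effects of socialization experiences on child skills at fall, winter, and spring". Inference is on their product: "Paths (a)\*(b) allow us to test the indirect effects of PRT on social, behavioral, and linguistic skills". The product is bootstrapped, and the only assumption discussed is normality of its sampling distribution.

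On adjustment, the Aim 1 text says: "In all models, we control for relevant covariates to increase precision of parameter estimates and power". For path (b) the plan gives no confounder set, no requirement that socialization be measured before skill, and no sensitivity analysis.

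Section III.d schedules the skill measures (TCRS, DPP, an expressive-language subtest) for focal children in fall, winter and spring. Section III.g does not name intervention status as a predictor of any of them. Aim 1 analyses interactions, play, talk and centrality, and Aim 3 analyses classroom network indices.

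**The concern.** Random assignment of classrooms protects path (a). It does not protect path (b), which relates two quantities observed in the same child over the same months. Anything other than PRT that makes a child's socialization and skill change together gives a non-zero (b). Once PRT also moves socialization, which is what Aim 1 hopes for, the product is non-zero even if PRT changed no skill. Bootstrapping improves the interval for the product but does not remove bias in (b).

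A mediation analysis always carries this assumption. Here, however, the product is the only planned evidence about skills. The one contrast that does not need the assumption, skill by randomised arm, is absent. At stake is whether Aim 2 can support any statement that PRT improved a skill.

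**Working it through.** The documents state no alpha, effect size, power or sample-size calculation for Aim 2, so there is no figure to reproduce. The check asks how often the product test rejects when PRT has no effect on skill.

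**Inputs.** Section III.a supports two Ohio allocations: 10 against 5 in each of two years, so 20:10, and a separate statement of 30 against 20. Both were run with one focal child per classroom. Assumed: path a of 0.5 to 1 SD, residual correlation r of 0 to 0.5, and a 95% percentile interval (two-sided 5%). All models are regression approximations to the latent growth model.

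**Step 1: the bias.** Let Z be arm, S = aZ + e_S and Y = e_Y, with unit variances and corr(e_S, e_Y) = r. The true effects of Z and S on Y are zero. Regressing Y on S and Z gives b → r, so the product tends to a × r instead of 0.
- a = 0.8, r = 0.5: 0.8 × 0.5 = 0.40. Simulated means are 0.39 (20:10) and 0.40 (30:20).
- a = 0.8, r = 0.3: 0.8 × 0.3 = 0.24. Simulated means are 0.24 and 0.23.

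**Step 2: false rejection without measurement error, direct PRT-to-skill path included.** The a = 1 rows give the range over repeated runs.

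| a (SD) | r | 20:10 | 30:20 |
|---|---|---|---|
| 0.5 | 0.3 | 10% | 20% |
| 0.5 | 0.5 | 21% | 44% |
| 0.8 | 0.3 | 22% | 44% |
| 0.8 | 0.5 | 42% | 77% |
| 1 | 0.3 | about 23–31% | 51–53% |
| 1 | 0.5 | 54–61% | 90–92% |

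With r = 0 or a = 0 the rate is at most about 7%. Omitting the direct path changes little: 42% and 73% at a = 0.8, r = 0.5.

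**Step 3: a stable common cause.** Here the shared cause acts equally at fall and winter (assumed retest correlation 0.8), at 20:10 with a = 1.
- No baseline adjustment: 26% (r = 0.3) and 61% (r = 0.5).
- Adjusted for fall skill: 8–13%.
- Adjusted for fall skill and fall socialization: 7–10%.

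In change-score models where only the baseline levels correlate, the rate is 2–4% at these two sizes. Adjustment therefore removes most of the excess from a stable cause.

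**Step 4: correlated change, with both baselines adjusted and measurement error.** With error SD 0.5 at each measurement, the variance of an observed change within arm is 1 + 2 × 0.5² = 1.5. Before baseline adjustment, the observed correlation of changes is therefore r/1.5, or 0.20 and 0.33 for r = 0.3 and 0.5. With a = 0.8, the product test rejects in 6% and 17% of trials at 20:10, and in 19% and 42% at 30:20.

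**Step 5: the randomised comparison.** In the same null trials, comparing the skill between arms rejects in 3–8%, whatever r is. Its power for a true 0.5 SD effect follows from the noncentrality 0.5 × √(n₁n₂/(n₁+n₂)):
- 20:10: 0.5 × √(200/30) = 1.29, power about 25%.
- 30:20: 0.5 × √(600/50) = 1.73, power about 41%.

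**The case against.** Four points on the other side have force.

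**Baseline adjustment.** A reader might infer that adjusting for fall values cannot help. That is not so. For a stable cause such as severity, Step 3 shows that adjustment removes most of the excess. Average maturation shared by all children is also absorbed by the mean slope. What remains is child-specific change in socialization and skill that moves together.

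**Evidence for correlated change.** A reader might take the Background as proof of a reverse path, since it says of exclusion and victimization: "These circumstances reflect in part the relatively poor social competence and pragmatic-language skills of children with LI". That sentence describes levels. It does not say that change in skill drives change in socialization within a school year, and nothing in the documents supports a particular r. The plan does, however, relate growth parameters of the two processes, so correlated change is the relevant condition.

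**The claim to be made.** A reader might infer that a significant product will be reported as a difference between arms on a skill. No section says so; the goals and Aim 2 speak of indirect or mediated effects. What stands is that Aim 2 sets out to determine PRT's contribution to skills and plans no other evidence for it.

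**The alternative is not clean either.** TCRS and DPP are completed by teachers, and under Intervention Implementation a classroom teacher or assistant delivers PRT. The rater may therefore know the condition and be the facilitator. The 3–8% in Step 5 does not include rater bias, and power is low at these sizes.

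**Conclusion.** The point holds in a bounded form. Aim 2 rests on a product whose second path is not randomised, and the skills are never compared between randomised arms. A false positive needs two things: PRT must move socialization, and child-specific changes in socialization and skill must correlate for reasons other than PRT. Given both, with r of 0.3 to 0.5, the illustrative rates are 6–17% (20:10) and 19–42% (30:20) with baselines adjusted and measurement error at a = 0.8 SD. Without measurement error at a = 1 SD they are about 23–61% and 51–92%. With small a and r at 20:10 the inflation is slight.

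The values of a, r, alpha and error SD are assumptions, and the models simplify the planned one. The simulations also treat path (a) as unconfounded, which would not hold if the non-randomised external control classrooms were pooled. The stronger reading, that the test will reject whenever socialization and skill are related, is not supported.

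**What to change.** In section III.g, Aim 2:

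1. For each skill, add the randomised fall-to-winter contrast in Ohio focal children: winter skill by assigned arm, adjusted for fall skill. Report its estimate and 95% CI beside every product, and base any statement that PRT improved a skill on it. Because wait-list classrooms start in spring, state that the winter assessment comes before that start.
2. Adjust path (b) for fall skill and fall socialization. Describe the product as conditional on no unmeasured common cause of the two changes. Report a sensitivity analysis with the residual correlation fixed at values from 0 to 0.5, giving the value at which the interval first includes zero. In simulation, fixing it at its true value brought rejection to 3–6%. The true value is unknown in practice, so a range is needed.
3. State that TCRS and DPP are teacher-rated and that the rater may be the facilitator, so the contrast in item 1 is open to rater bias on these measures.

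The cost is protocol wording, one regression per skill and one sensitivity run per mediation model, on data already planned. The downside is a wide interval for the total effect (about 25% power for 0.5 SD at 20:10) and a more guarded mediation claim.
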